## **6.5 POOLING OF CENTRES**

This section is not applicable, because the study was performed in only one centre.

## **6.6 HANDLING OF MISSING DATA AND OUTLIERS**

Handling of missing data and outliers will be performed as described in the CTP, Section 7.4.

The only exceptions where imputation might be necessary for safety evaluation are AE dates. Missing or incomplete AE dates are imputed according to BI standards (see 001-MCG-156\_RD-01 ([4](#))).

Missing data and outliers of PK data are handled according to BI standards (see 001-MCS-36-472\_RD-01) ([5](#)).

## **6.7            BASELINE, TIME WINDOWS AND CALCULATED VISITS**

The baseline value is defined as the last measurement before administration of BI 1323495 or Placebo.

**Section 6.1 of the CTP:** *Exact times of measurements outside the permitted time windows will be documented. The acceptable time windows for screening and end of trial examination are given in the CTP Flow Chart.*

*Study measurements and assessments scheduled to occur 'before' trial medication administration on Day 1 are to be performed and completed within a 3 h-period prior to the trial drug administration (including blank values for PK and biomarkers).*

Adherence to time windows will be checked via the consistency check listings at the RPM/DBLM.

## **7. PLANNED ANALYSIS**

The placebo group in the safety evaluation will consist of all placebo treated subjects, regardless of the dose group in which they were treated.

Safety analysis (refer to [Section 7.8](#)) will be performed by and will be presented in Sections 15.1 to 15.4 of the CTR and in Appendix 16.2 and 16.1.13.1.

Descriptive data analysis of PD parameters will be performed by and will be presented in Sections 15.7 of the CTR.

Inferential statistical analyses of PK and PD endpoints (refer to [Section 7.5.2](#)) will also be performed by and will be presented in Section 15.5, and 15.7 of the CTR and in Appendices 16.1.13.3 and 16.1.13.6.

Descriptive data analysis of PK parameters and concentrations will be performed by the department Translational Medicine and Clin. Pharmacology at BI and will be presented in Section 15.6 and 15.7 of the CTR.

The format of the listings and tables will follow the standards defined in the BI corporate guideline “Reporting of Clinical Trials and Project Summaries” [001-MCG-159] (6) with the exception of those generated for PK-calculations.

The individual values of all subjects will be listed, sorted by treatment group, subject number, and visit.

The listings will be included in Appendix 16.2 of the CTR.

For end-of-text tables, the set of summary statistics for non-PK parameters is:

N	number non-missing observations
Mean	arithmetic mean
SD	standard deviation
Min	minimum
Median	median
Max	maximum

For analyte concentrations, the following descriptive statistics will additionally be calculated:

CV	arithmetic coefficient of variation
gMean	geometric mean
gCV	geometric coefficient of variation

For PK parameters, the following descriptive statistics will additionally be calculated:

CV	arithmetic coefficient of variation
gMean	geometric mean
gCV	geometric coefficient of variation
P10	10th percentile
Q1	1st quartile
Q3	3rd quartile
P90	90th percentile

The data format for descriptive statistics of concentrations will be identical with the data format of the respective concentrations. The descriptive statistics of PK parameters will be calculated using the individual values with the number of decimal places as provided by the evaluation program. Then the individual values as well as the descriptive statistics will be reported with three significant digits in the CTR.

Tabulations of frequencies for categorical data will include all possible categories and will display the number of observations in a category, as well as the percentage (%) for each treatment group. Percentages will be rounded to one decimal place and will be based on all subjects in the respective subject set whether they have non-missing values or not. The category 'missing' will be displayed only if there are actually missing values.

Units of variables should be given in the titles or column/row descriptors in square brackets (e.g. [mg]).

#### Exclusion of PK parameters

The ADS ADPP (PK parameters) contains column variables APEXC and APEXCO indicating inclusion/exclusion (APEXC) of a PK parameter and an analysis flag comment (APEXCO). All analyses based on the PKS will include parameters if they are not flagged for exclusion, that is APEXC is equal to "Included".

#### Exclusion of PK concentrations

The ADS ADPC (PK concentrations per time-point or per time-interval) contains column variables ACEXC or ACEXCO indicating inclusion/exclusion (ACEXC) of a concentration and an analysis flag comment (ACEXCO). Exclusion of a concentration depends on the analysis flag comment ACEXCO. For example, if ACEXCO is set to 'ALL CALC', the value will be excluded for all types of analyses based on concentrations. If ACEXCO is set to 'DESC STATS', the value will be excluded from descriptive evaluations per planned time point/time interval. If ACEXCO contains the addition 'TIME VIOLATION' or 'TIME DEVIATION', the value can be used for further analyses based on actual times. If ACEXCO is set to 'HALF LIFE', the value will be excluded from half-life calculation (and, as a consequence, any calculation that relies on  $\lambda_z$ ) only; the value is included for all other analyses.

Further details are given in 001-MCS-36-472\_RD-01 “Noncompartmental Pharmacokinetic / Pharmacodynamic Analyses of Clinical Studies” ([5](#)) and 001-MCS-36-472\_RD-03 “Description of Analytical Transfer Files and PK/PD Data Files” ([7](#)).

## **7.1 DEMOGRAPHIC AND OTHER BASELINE CHARACTERISTICS**

Only descriptive statistics are planned for this section of the report, based on the TS.

The data will be summarised by treatment group and in total.

## **7.2 CONCOMITANT DISEASES AND MEDICATION**

Frequency tables are planned for this section of the report, based on the TS.

Concomitant diseases will be coded using the latest version of the coding system of the Medical Dictionary for Drug Regulatory Activities (MedDRA). Medications will be coded using the latest version of the World Health Organization Drug Dictionary (WHO-DD). The coding version number will be displayed as a footnote in the respective output.

The diagnoses and medications will be listed. Subjects without any concomitant diagnoses or concomitant therapies should be marked with a “No” in the respective column.

The relevance of the concomitant therapies to the evaluation of PK will be decided no later than at the RPM/DBLM.

## **7.3 TREATMENT COMPLIANCE**

**Section 4.3 of the CTP:** *Compliance will be assured by administration of all trial medication in the study centre under supervision of the investigating physician or a designee. The measured plasma concentrations will provide additional confirmation of compliance.*

It is not intended to list the compliance separately. Any deviations from complete intake will be addressed in the RPM/DBLM (cf. TSAP [Section 6.2](#)) and described in the CTR.

## **7.4 PRIMARY ENDPOINTS**

Refer to TSAP [Section 7.8](#) for a description of the analysis of safety and tolerability of BI 1323495.

## **7.5 SECONDARY ENDPOINTS**

### **7.5.1 Key secondary endpoints**

This section is not applicable as no key secondary endpoints have been specified in the protocol.

### **7.5.2 Secondary endpoints**

#### **Section 7.3.2 of the CTP:**

##### *Assessment of dose proportionality*

Dose proportionality will be assessed using the pharmacokinetic endpoints as specified in [Section 5.2.2](#)

*Based on the estimate for slope parameter ( $\beta$ ), a 2-sided 90% CI for the slope will be computed. Perfect dose proportionality would correspond to a slope of 1. The assumption of a linear relationship between the log-transformed pharmacokinetic endpoint and the log-transformed dose will be checked.*

*If dose proportionality over the entire dose range investigated cannot be shown, an attempt will be made to identify dose range(s), where dose proportionality can be assumed.*

This analysis will be accomplished by using the XPKISTAT macro (design DB), based on the PKS.

Graphical displays:

A regression plot will be performed, where the logarithm of dose is depicted versus logarithm of PK endpoint, including the estimated regression line from the power model and reference line of perfect proportionality ( $\beta=1$ ).

## **7.7 EXTENT OF EXPOSURE**

Descriptive statistics are planned for this section of the report based on the TS. The date and time of drug administration will be listed for each subject.

## **7.8 SAFETY ANALYSIS**

All safety analyses will be performed on the TS.

If not stated otherwise, the safety results will be sorted by treatment group.

The safety data for treated subjects who failed to complete the study (dropouts or withdrawals) will be reported as far as their data are available. All withdrawals will be documented and the reason for withdrawal recorded.

### **7.8.1 Adverse events**

AEs will be coded with the most recent version of MedDRA.

The analyses of AEs will be descriptive in nature and will be based on BI standards as presented in the corporate guideline: “Analysis and Presentation of Adverse Event Data from Clinical Trials” [001-MCG-156] ([9](#)).

The standard AE analyses will be based on the number of subjects with AEs (and not on the number of AEs).

For analysis multiple AE occurrence data on the CRF will be collapsed into an AE provided that all of the following applies:

- All AE attributes are identical (lower level term (LLT), intensity, action taken, therapy required, seriousness, reason for seriousness, relationship, outcome, AE of special interest)
- The occurrences were time-overlapping or time-adjacent (time-adjacency of two occurrences is given if the second occurrence started within one hour after end of the first occurrence)

For further details on summarization of AE data, please refer to [001-MCG-156] (9).

**Section 5.2.2.1 of the CTP: The following are considered as AESIs:**

- Hepatic injury  
*A hepatic injury is defined by the following alterations of hepatic laboratory parameters:*
  - *an elevation of AST (aspartate aminotransferase) and/or ALT (alanine aminotransferase)  $\geq 3$ -fold ULN combined with an elevation of total bilirubin  $\geq 2$ -fold ULN measured in the same blood sample, or*
  - *aminotransferase (ALT, and/or AST) elevations  $\geq 10$  fold ULN*

*These lab findings constitute a hepatic injury alert, and the subjects showing these lab abnormalities need to be followed up according to the 'DILI checklist' provided in the ISF. In case of clinical symptoms of hepatic injury (icterus, unexplained encephalopathy, unexplained coagulopathy, right upper quadrant abdominal pain, etc.) without lab results (ALT, AST, total bilirubin) available, the Investigator should make sure that these parameters are analysed, if necessary in an unscheduled blood test. Should the results meet the criteria of hepatic injury alert, the procedures described in the DILI checklist should be followed.*

The analysis of adverse events will be based on the concept of treatment emergent adverse events.

**Section 7.3.3 of the CTP: The REP for BI 1323495, the time interval when measurable drug levels or PD effects are still likely to be present after administration, is not known for this first-in-human trial. Therefore, all AEs with an onset between start of treatment and the end of trial examination (last per protocol contact) will be considered on treatment.**

According to ICH E3 ([10](#)), AEs classified as 'other significant' needs to be reported and will include those non-serious and non-significant adverse events with  
(i) 'action taken = discontinuation' or 'action taken = reduced', or  
(ii) marked haematological and other lab abnormalities or lead to significant concomitant therapy as identified by the Clinical Monitor/Investigator at the RPM at the latest.

An overall summary of AEs (including AESIs) will be presented.

The frequency of subjects with AEs will be summarized by treatment, primary system organ class (SOC) and preferred term (PT). Separate tables will be provided for subjects with other significant AEs according to ICH E3 ([10](#)), for subjects with serious AEs, for subjects with drug-related AEs, for subjects with drug related serious adverse events and for subjects with AESIs.

The SOC and PTs will be sorted by frequency (within SOC). The MedDRA version number will be displayed as a footnote in the respective output.

In addition, frequencies of subjects with non-serious AEs that had an incidence of  $> 5\%$  for at least one treatment will be summarised by treatment, primary SOC and PT.

For disclosure of adverse events on EudraCT additional information not included in a standard AE analysis will be performed. The following three entries will be created:

- Adverse Events per arm for disclosure on EudraCT
- Non-serious Adverse Events for disclosure on EudraCT
- Serious Adverse Events for disclosure on EudraCT

### **7.8.2      Laboratory data**

The analyses of laboratory data will be descriptive in nature and will be based on BI standards [001-MCG-157] ([11](#)). Tables and listings will be based on standardized values only.

Laboratory data will be analysed qualitatively via comparison of laboratory data to their reference ranges. Values outside the reference range as well as values defined as possible clinically significant will be flagged in the data listings.

It is the investigator's responsibility to decide whether a lab value is clinically significant abnormal or not (at the RPM/DBLM at the latest).

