7.3.3 Safety analyses

Safety will be assessed for the endpoints and parameters of interest listed in [Section 5.2.1](#). All treated subjects (that is, all subjects who received at least one dose of study drug), will be included in the safety analysis. For additional analyses sets used in the ECG evaluation see TSAP for further details. Safety analyses will be descriptive in nature and will be based on BI standards. No hypothesis testing is planned.

Treatments will be compared in a descriptive way. The placebo control group in the safety evaluation will consist of all placebo treated subjects, regardless of the dose group in which they were treated. The active treatment groups will be compared to the placebo group in a descriptive way. Tabulations of frequencies/proportions will be used for the evaluation of categorical (qualitative) data, and tabulations of descriptive statistics will be used to analyse continuous (quantitative) data.

The analyses will be done by ‘treatment at onset’.

The REP for BI 1323495, the time interval when measurable drug levels or PD effects are still likely to be present after administration, is not known for this first-in-human trial. Therefore, all AEs with an onset between start of treatment and the end of trial examination (last per protocol contact) will be considered on treatment.

Measurements (such as ECG, vital signs, or laboratory parameters) or AEs will be assigned to treatments (see [Section 4.1](#)) based on the actual treatment at the planned time of the measurement or on the recorded time of AE onset (concept of treatment emergent AEs).

Therefore, measurements planned or AEs recorded prior to intake of trial medication will be assigned to 'screening' and those between trial medication intake until the end of trial visit will be assigned to the treatment period. These assignments including the corresponding time intervals will be defined in detail in the TSAP. Please note that AEs occurring after the last per protocol contact but entered before database lock will be reported to drug safety only and will not be captured in the trial database.

Additionally, further treatment intervals (analysing treatments) may be defined in order to provide summary statistics for time intervals, such as combined treatments, on-treatment totals or periods without treatment effects (such as screening and post-study intervals).

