Adverse events will be coded using the Medical Dictionary for Regulatory Activities (MedDRA). Frequency, severity, and causal relationship of AEs will be tabulated by treatment, system organ class, and preferred term. SAEs, AESIs (see [Section 5.2.2.1](#)), and other significant AEs (according to ICH E3) will be listed separately.

Laboratory data will be compared to their reference ranges. Values outside the reference range as well as values defined as clinically relevant will be highlighted in the listings. Additionally, differences from baseline will be evaluated.

Vital signs or other safety-relevant data observed at screening, baseline, during the course of the trial and at the end-of-trial evaluation will be assessed with regard to possible changes compared to findings before start of treatment.

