#### **4. CHANGES IN THE PLANNED ANALYSIS OF THE STUDY**

All analyses as planned in the CTP will be performed and are described in more detail in this TSAP. The following changes compared to the protocol will be made:

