Tables of vital signs and laboratory values will present results by the above mentioned on treatment phase.

For detailed information on the handling of the treatments refer to Technical TSAP ADS (analysis data set) plan and Data Reviewers guide.

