### **7.8.3      Vital signs**

Descriptive statistics over time including change from baseline will be performed for vital signs (blood pressure and pulse rate).

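### Does SAP 7.8.2 drop the laboratory differences from baseline that protocol 7.3.3 plans?

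*SAP*

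**What the plan says.** Protocol 7.3.3 gives three elements for laboratory data: comparison with reference ranges, highlighting of out-of-range and clinically relevant values in the listings, and a further step, "Additionally, differences from baseline will be evaluated". The same section sets a general rule for safety data, that "tabulations of descriptive statistics will be used to analyse continuous (quantitative) data", with active groups set descriptively beside placebo.

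SAP 7.8.2 calls the laboratory analysis descriptive, bases it on the sponsor standard 001-MCG-157, and mentions tables and listings of standardized values. The one analysis it spells out is "Laboratory data will be analysed qualitatively via comparison of laboratory data to their reference ranges", together with flags in the listings. SAP 7.8.3, directly after it, says "Descriptive statistics over time including change from baseline will be performed for vital signs".

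Other SAP sections bear on the point:
- SAP 4: "All analyses as planned in the CTP will be performed and are described in more detail in this TSAP".
- SAP 6.1: "Tables of vital signs and laboratory values will present results by the above mentioned on treatment phase".
- SAP 6.7: "The baseline value is defined as the last measurement before administration of BI 1323495 or Placebo".
- SAP 7: N, mean, SD, minimum, median and maximum for end-of-text tables of non-PK parameters, all placebo subjects pooled, and "The individual values of all subjects will be listed, sorted by treatment group, subject number, and visit".

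**The concern.** Two of the protocol's three laboratory elements reappear in SAP 7.8.2 and one does not. The word *qualitatively* makes this look like more than silence, because a programmer who read that section alone could deliver range flags and nothing else. The contrast with SAP 7.8.3 sharpens the impression: where the SAP wants change from baseline, it says so.

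Safety is the primary objective of this first-in-human trial, and laboratory tests are a named safety criterion in protocol 5.2.1. Exclusion criteria 25 and 27 admit only men with an eGFR of at least 90 mL/min and with ALT, AST and GGT not above the upper limit, so a modest drug effect could stay inside the reference range. If flags and listings were all that was produced, such a shift would be hard to see in a group of 6.

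**Working it through.** **Is the analysis removed or only not restated?** Taking the elements in turn:

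| Element | Protocol 7.3.3 | SAP |
|---|---|---|
| Reference-range comparison | planned | 7.8.2 |
| Flags in listings | planned | 7.8.2 |
| Differences from baseline | planned | not named for laboratory data; covered by the general commitment in SAP 4 |
| Baseline definition | – | 6.7, not restricted by data type |
| Pooled placebo comparator | planned | 6.1 and 7 |
| Summary statistics | planned for continuous data | 7, for non-PK end-of-text tables |
| Laboratory tables by treatment phase | – | 6.1 |

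SAP 3 adds that the SAP rests on protocol Section 7 and assumes the reader knows it. Everything needed to produce the differences is defined. Only the sentence naming them in 7.8.2 is missing.

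**How much could be lost?** The documents give no laboratory SDs, so this is an illustration. Assumptions: normal values, a reference SD of 1, a central 95% reference range, and a within-subject SD *w* of 0.5 (range 0.3 to 0.7). From the documents: 6 active subjects per group and 8 × 2 = 16 pooled placebo subjects.

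*Range flags only, one parameter at one time point.* P(above upper limit) = 1 − Φ(1.96 − shift), which is 0.025, 0.072 and 0.169 for shifts of 0, 0.5 and 1 SD. P(no flag among 6) = (1 − p)^6, which is 0.86, 0.64 and 0.33.

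*Mean change from baseline, 6 against 16.* SE = w × √2 × √(1/6 + 1/16) = w × √2 × 0.479, which is 0.203, 0.339 and 0.474 for w = 0.3, 0.5 and 0.7.

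*Mean on-treatment value, 6 against 16.* SE = √(1/6 + 1/16) = 0.479.

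| Shift | Shift/SE, raw means | Shift/SE, change (w = 0.3 / 0.5 / 0.7) |
|---|---|---|
| 0.5 SD | 0.5/0.479 = 1.0 | 2.5 / 1.5 / 1.1 |
| 1 SD | 1/0.479 = 2.1 | 4.9 / 3.0 / 2.1 |

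Set against flags alone, change from baseline looks valuable: a 1 SD shift leaves a group without a high flag about one time in three. But SAP 6.1 plans laboratory tables and SAP 7 gives means for non-PK tables, so the fairer comparator is the raw mean beside placebo. The ratio of the two SEs is w√2. The gain therefore vanishes at w = 1/√2 = 0.71 and is nearly nil at 0.7. It is real when within-subject variation is small.

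The flag figures also cover a single sample. Blood is taken repeatedly, including at 4 h on Day 1 (footnote to Table 5.2.3: 1) and at the end of trial, so the chance of no flag at any time is lower than shown. For liver enzymes the entry limit works the other way and makes a flag rarer.

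**The case for a change.** The strongest case for a change is that SAP 4 promises not only to perform the protocol's analyses but to describe them in more detail, and on this point the SAP is less detailed than the protocol. The content of 001-MCG-157 is not in the documents, so nobody can confirm that it yields change-from-baseline tables. None of the planned tables or listings is expressly said to show laboratory change. The trial is single-blind with an open-label database, which favours fixing outputs in advance. One sentence would settle it from data already collected.

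The textual part stands: SAP 7.8.2 does not restate the evaluation, and *qualitatively* is an awkward word beside the protocol's rule for continuous data. The visible text of SAP 4 also stops before any list of changes, so a declared change in removed text cannot be excluded.

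The step from there to a lost analysis does not stand. The unseen standard cuts both ways: it may already give the output, in which case the remedy would be only a cross-reference. With no declared change in view, the commitment in SAP 4 governs.

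**Conclusion.** This is a gap that analysts fill sensibly, and no change to the plan follows. Protocol 7.3.3 still binds through SAP 4, and the baseline, comparator and summary statistics are already defined, so following the two documents together yields the laboratory differences from baseline.

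Even if the tables came out without them, the loss would be modest. A 1 SD shift would sit at 2.1 standard errors on raw means instead of 2.1 to 4.9, and individual values by visit would let anyone derive the differences. These figures rest on assumed SDs and normality, and on reading SAP 6.1 and 7 as giving laboratory means by treatment. The wording favours that reading but does not prove it.

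The primary endpoint is the number of subjects with drug-related adverse events and is not affected, nor are the pharmacokinetic endpoints. Clinically relevant laboratory changes are recorded as adverse events (protocol 5.2.2.1), hepatic alerts are events of special interest, and laboratory results are reviewed before every escalation (protocol 3.1). No hypothesis is tested on laboratory data.
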